4.4. Secondary Endpoint(s) Analysis

4.4.1. Key Secondary Endpoints

The endpoints corresponding to secondary study objectives subject to type 1 error rate control are specified in Section 1.1 under “Key Secondary (Controlled for Type 1 error) endpoints”.

The alternative hypotheses corresponding to the key secondary objectives can be found in Section 2.

Key secondary objectives will be evaluated based on the treatment-regimen and the efficacy estimands (Section 1.1), similar to the primary objective.

4.4.1.1. Mean change in HbA1c from Baseline at the 40-week visit

Assessment of superiority of mean changes in HbA1c of tirzepatide 5 mg compared with placebo at Week 40 will be conducted using the same statistical models as those used for evaluating the primary objective in Section 4.3.2 (efficacy estimand) and Section 4.3.3 (treatment-regimen estimand). Two-sided p-values will be reported for comparisons between tirzepatide and placebo. Inferences will be made based on the multiplicity testing framework outlined in Section 2.1.

4.4.1.2. Mean Change in Body Weight from Baseline at the 40-week Visit

The analysis for change in body weight from baseline (postbaseline - baseline) at Week 40 will be conducted in a manner similar to the primary analysis in Section 4.3.2 (efficacy estimand) and Section 4.3.3 (treatment-regimen estimand) with the following differences:

- For the efficacy estimand, the MMRM model (Section 4.3.2) will be updated by adding the baseline category for HbA1c ($\leq 8.0\%$, $>8.0\%$) as a fixed factor in place of baseline HbA1c, and baseline weight as an additional covariate.
- For the treatment-regimen estimand, the ANCOVA model (Section 4.3.3), baseline category for HbA1c ($\leq 8.0\%$, $>8.0\%$) will be used as a fixed factor in place of baseline HbA1c as a covariate and baseline weight will be used as an additional covariate in the statistical model. Imputation of missing values at either Week 40 will be done in a similar manner as described in Section 4.3.4. If value of the imputed weight change from

baseline is <-50 kg or >50 kg, that value will be set to -50 kg or 50 kg, respectively, to avoid unrealistic imputed values.

4.4.1.3. Mean change in FSG from Baseline at the 40-week Visit

The analysis for change in FSG from baseline (postbaseline - baseline) at Week 40 will be conducted in a manner similar to the primary analysis in Section 4.3.2 (efficacy estimand) and Section 4.3.3 (treatment-regimen estimand) with the following differences:

- For the efficacy estimand, the MMRM model (Section 4.3.2) will be updated by adding the baseline category for HbA1c ($\leq 8.0\%$, $> 8.0\%$) as a fixed factor in place of baseline HbA1c, and baseline FSG as an additional covariate.
- For the treatment-regimen estimand, the ANCOVA model (Section 4.3.3), baseline category for HbA1c ($\leq 8.0\%$, $> 8.0\%$) will be used as a fixed factor in place of baseline HbA1c as a covariate and baseline FSG will be used as an additional covariate in the statistical model. Imputation of missing values at either Week 40 will be done in a similar manner as described in Section 4.3.4. If value of the imputed fasting serum glucose change from baseline is <-20 mmol/L or > 20 mmol/L, that value will be set to -20 mmol/L or 20 mmol/L, respectively, to avoid unrealistic imputed values.

4.4.1.4. Proportion of participants with HbA1c <7.0%, $\leq 6.5\%$, <5.7%

The analysis for binary outcomes relative to the “efficacy” estimand will be performed using EAS with missing values imputed by the predicted value from the MMRM model specified in Section 4.3.2 and dichotomized data will then be derived based on continuous imputed values. After dichotomizing, the data is analyzed using a logistic regression model which include treatment, SGLT-2i use (Yes or No) as fixed effects, and baseline HbA1c as covariates. In addition, analysis will be conducted utilizing data using EAS from baseline through the 40-week visit with the aid of a longitudinal logistic regression with repeated measurements with treatment, visit, treatment-by-visit interaction and SGLT-2i use (Yes/No) as fixed effects and baseline HbA1c as a covariate. In case the longitudinal logistic model does not converge due to small number of events, logistic regression will be utilized to analyze proportion of patients achieving HbA1c targets at nominal visits.

The analysis for binary outcomes relative to the “treatment-regimen” estimand will be performed using FAS at baseline and at the 40-week visits with the aid of a logistic regression with multiple imputation of missing data at the 40-week visit (see Section 4.3.4 for details) and dichotomized data will then be derived based on continuous imputed values. After dichotomizing, the data is analyzed using a logistic regression model which include treatment, SGLT-2i use (Yes or No) as fixed effects, and baseline HbA1c as covariates. Statistical inference over multiple imputations will be guided by Rubin (1987).

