8.3.4.2. Severe, Persistent Hyperglycemia

Severe, persistent hyperglycemia will be collected during the trial to assess the risk of extreme imbalance in glycemic control.

Investigators will be trained on the application of criteria for deciding when and how to intervene with participants who do not reach glycemic targets. An additional therapeutic intervention should be considered in participants who develop severe, persistent hyperglycemia after randomization at the discretion of investigator in accordance with American Diabetes Association/European Association for the Study of Diabetes guidance (Inzucchi et al. 2015). Rescue medication will be prescribed as add-on to randomized treatment, and participants will continue to follow the protocol-specified visit schedule.

Because insulin glargine dose adjustments without restrictions will be initiated at the end of the stabilization period (see Section 4.1), decision on the presence of severe, persistent hyperglycemia can be first considered 12 weeks after the initiation of this period (approximately 16 weeks after randomization).

Add-on glycemic rescue therapy will be allowed for participants who met any one of the following prespecified criteria for severe, persistent hyperglycemia and no intercurrent cause of the hyperglycemia could be identified (investigators should first confirm that the participant is

fully compliant with the assigned therapeutic regimen and that the participant does not have an acute condition causing severe hyperglycemia):

- a) Average daily BG from the once weekly 4-point SMBG profile >13.3 mmol/L (>240 mg/dL) over a consecutive 2-week period at any time 16 to 24 weeks post randomization.

OR

- b) Average daily BG from the once weekly 4-point SMBG profile >11.1 mmol/L (>200 mg/dL) over a consecutive 2-week period at any time beyond the first 24 weeks post randomization.

OR

- c) HbA1c $\geq 8.5\%$ at 24 weeks, AND with inadequate response to the existing regimen defined as improvement in HbA1c over the last 3 months (Week 12 to Week 24) that is, $<0.3\%$

Rescue therapy option:

The criteria described above for severe, persistent hyperglycemia will only be applicable after Week 16. The first choice before initiating any rescue therapy for those participants during the initial 16 weeks will be to follow the TTT algorithm to increase the dose of insulin glargine.

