- *Population-level summary:* Difference in mean changes between treatment conditions.

Secondary estimand

The treatment-regimen estimand answers the following question of interest for the primary objective: What is the treatment difference in change from baseline in HbA1c after 40 weeks of treatment in participants with T2DM regardless of treatment discontinuation for any reason and regardless of initiation of antihyperglycemic rescue?

The treatment-regimen estimand is described by the following attributes.

[figure not shown]
- *Population:* Participants with T2DM inadequately controlled on insulin glargine alone or in combination with metformin with or without SGLT-2i.
- *Endpoint:* Change from baseline to week 40 after randomization in HbA1c.
- *Treatment condition:* The randomized treatment regardless of adherence to treatment with or without antihyperglycemic rescue medication.
- *Intercurrent events:* “Permanent discontinuation from treatment for any reason” and “initiation of rescue antihyperglycemic treatment” are addressed by the treatment condition.
- *Population-level summary:* Difference in mean changes between treatment conditions.

Both the efficacy and treatment-regimen estimands will be evaluated for the primary and all key secondary objectives. The population, treatment condition, and intercurrent events specified above for each estimand for the primary objective will also apply to the key secondary objectives. The endpoint for each key secondary objective is defined in the table above.

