2.1. Multiplicity Adjustment

Since they are intended for different purposes, no type I error rate adjustments will be made for conducting analyses relative to “efficacy” and “treatment-regimen” estimands. For analyses within each estimand, the type I error control strategy for evaluation of primary and key secondary objectives is illustrated in [Figure GPIM.2.1](#).

1. $H_{15,1}$, $H_{15,2}$, are evaluated hierarchically each at a 2-sided 0.025 significance level conditioned on successfully achieving the preceding objective. In parallel,
2. $H_{10,1}$, $H_{10,2}$ are evaluated hierarchically each at two-sided 0.025 significance level conditioned on successfully achieving the preceding objective.
3.
 - a) If all objectives in #1 and #2 above are successfully established, $H_{5,1}$, $H_{5,2}$ are evaluated hierarchically, each at a 2-sided 0.05 significance level.
 - b) If all objectives in only #1 or only #2 above are successfully established, $H_{5,1}$, $H_{5,2}$ are evaluated hierarchically, each at a 2-sided 0.025 significance level.
4. If all objectives: $H_{5,1}$, $H_{5,2}$ are successfully established and
 - a) if all objectives in #1 and #2 above are successfully established, then $H_{15,3}$, $H_{10,3}$, $H_{5,3}$, $H_{15,4}$, $H_{10,4}$, $H_{5,4}$, $H_{15,5}$, $H_{10,5}$, $H_{5,5}$, $H_{15,6}$, $H_{10,6}$ and $H_{5,6}$ will be evaluated hierarchically each at two-sided 0.05 significance level conditioned on the successfully achieving the preceding objective.
 - b) If all objectives in only #1 or only #2 above are successfully established, then $H_{15,3}$, $H_{10,3}$, $H_{5,3}$, $H_{15,4}$, $H_{10,4}$, $H_{5,4}$, $H_{15,5}$, $H_{10,5}$, $H_{5,5}$, $H_{15,6}$, $H_{10,6}$ and $H_{5,6}$ will be

- c) evaluated hierarchically each at a 2-sided 0.025 significance level conditioned on successfully achieving the preceding objective.

5. If all objectives in #3 and #4 above are successfully established, and at least 1 objective from #1 or #2 above is not successfully established, recycle 100% of the unused alpha back to #1 or #2 above.

[figure not shown]

Figure GPIM.2.1

Type I Error control strategy for primary and key secondary efficacy endpoints.

3. Analysis Sets

Table GPIM.3.1 defines the analysis population and datasets for the purposes of analysis based on the estimands defined in Section 1.1.

Table GPIM.3.1. Analysis Populations/Data Sets

Population/Analysis Set	Description
Screened population	All participants who signed informed consent.

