Randomized population	All participants who are randomly assigned to a treatment group.
Modified intent-to-treat population (mITT)	All randomly assigned participants who are exposed to at least 1 dose of study intervention. Participants will be analyzed according to the treatment they were randomly assigned to regardless of the treatment actually received.
Efficacy Analysis Set: This analysis set will be used to estimate the efficacy estimand for the primary and key secondary objectives	Data obtained during the Treatment Period from the mITT population, excluding participants discontinuing study drug due to inadvertent enrollment, excluding data after permanent discontinuation of treatment or initiation of antihyperglycemic rescue medication.
Full Analysis Set: This analysis set will be used to estimate the treatment-regimen estimand for the primary and key secondary objectives	Data obtained during the treatment period from the mITT population, excluding participants discontinuing study drug due to inadvertent enrollment, regardless of adherence to treatment or initiation of antihyperglycemic rescue medication.
Safety Analysis Set (SS): This analysis will be used to assess the safety of study treatment	Data obtained during the Treatment Period plus Safety Follow-Up from the mITT population, regardless of adherence to treatment or initiation of antihyperglycemic rescue antihyperglycemic medication.

4. Statistical Analyses

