4.10. Changes to Protocol-Planned Analyses

NA

5. Sample Size Determination

Participants will be randomized in a 1:1:1:1 ratio to tirzepatide 5 mg, 10 mg, 15 mg, or placebo. The trial is powered to assess superiority of tirzepatide 10 mg and 15 mg, each tested in parallel, against placebo at a 2-sided significance level of 0.025, relative to the primary endpoint (mean change in HbA1c from baseline to 40 weeks), under the following assumptions: use of a 2-sample t-test utilizing HbA1c data collected before initiation of any rescue medication or premature treatment discontinuation with no more than 25% of participants initiating rescue medication or prematurely discontinuing treatment in each treatment group; 0.95% greater mean reduction in HbA1c from baseline for 10 and 15 mg tirzepatide compared with placebo; 1:1:1:1 randomization; and a common standard deviation (SD) of 1.3%. On the basis of these assumptions, a sample size of 256 participants is required to ensure at least 90% power to demonstrate that tirzepatide 10 mg and/or 15 mg are superior to placebo relative to the primary endpoint.

Assignment to treatment arms will be determined by a computer-generated random sequence using an interactive web response system (IWRS). Patients will be randomized in a 1:1:1:1 ratio to receive 5 mg tirzepatide, 10 mg tirzepatide, 15 mg tirzepatide, or placebo. The randomization will be stratified by baseline HbA1c concentration ($\leq 8.0\%$, $> 8.0\%$ [≤ 64 , > 64 mmol/mol]), and SGLT-2i use (Yes/No).

6. Supporting Documentation

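### The efficacy-estimand HbA1c responder tests analyse one MMRM prediction per missing Week 40 value as if observed; with substantial missingness and a placebo mean near the cut-off, this inflates per-test type I error and biases the responder difference

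*SAP*

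**What the plan says.** SAP 1.1 applies both estimands to every alpha-controlled objective: "Both the efficacy and treatment-regimen estimands will be evaluated for the primary and all key secondary objectives". For the efficacy estimand, the Efficacy Analysis Set in SAP Section 3 is defined by "excluding data after permanent discontinuation of treatment or initiation of antihyperglycemic rescue medication", so anyone who stops treatment or is rescued has no usable Week 40 HbA1c.

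SAP 4.4.1.4 then gives two efficacy-estimand analyses of the proportions at <7.0%, ≤6.5% and <5.7%:

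- The first works on a data set with "missing values imputed by the predicted value from the MMRM model specified in Section 4.3.2". The completed value is dichotomised and analysed by logistic regression on treatment, SGLT-2i use and baseline HbA1c. No residual draw, repeated imputation or variance correction is mentioned.
- The second is introduced with "In addition, analysis will be conducted utilizing data using EAS from baseline through the 40-week visit with the aid of a longitudinal logistic regression". It does not use the filled values.

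For the treatment-regimen estimand, the same section prescribes multiple imputation with Rubin's rules. SAP 4.4.2.2 repeats the single-prediction rule for the additional secondary binary endpoints, including weight loss, although the 4.3.2 model has HbA1c change as its response.

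The responder hypotheses are in step 4 of SAP 2.1. They are tested at 0.05 if both high-dose branches are won, and at 0.025 on the route headed "If all objectives in only #1 or only #2 above are successfully established".

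**The concern.** A predicted mean is not a plausible observed value. Cutting it at a threshold turns a probability near one half into a certain yes or no. Two consequences follow. First, a small chance difference between fitted arm means can move many filled participants across the cut-off together, and the logistic model counts each as an independent observation, so its standard error is too small. Second, the filled responder share differs from the true share whenever the predictions sit mainly on one side of the cut-off, so the reported difference is biased even when the test is won.

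These endpoints are alpha-controlled and their differences will be reported. The documents give no expected Week 40 placebo mean, so direction and size cannot be fixed from them. The SAP also leaves open whether the prediction is conditional on the participant's earlier HbA1c or marginal (arm and covariates only), and the size depends on which is meant.

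**Working it through.** **Sizing inputs.** SAP Section 5 gives 64 per arm, SD of change 1.3, effect 0.95, two-sided alpha 0.025, and "no more than 25% of participants initiating rescue medication or prematurely discontinuing treatment in each treatment group". Evaluable per arm: 64 × 0.75 = 48. Standard error: 1.3 × √(2/48) = 0.265; noncentrality 0.95 / 0.265 = 3.58. The two-sample t-test has power 0.902, so the stated 90% with 256 participants is reproduced. The documents give no error rate or power for the responder endpoints.

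**Mechanism in one calculation.** Assume a residual SD of 1.18 and correlation 0.85 between visits 8 weeks apart. For someone last seen at Week 32, the conditional SD at Week 40 is 1.18 × √(1 − 0.85²) = 0.62. With predictions of 7.2 and 6.8, the chance of a value below 7.0 is Φ(−0.2/0.62) = 0.37 and Φ(0.2/0.62) = 0.63. The single-value rule records 0 and 1. A 26-point difference in probability becomes 100 points. With marginal prediction (SD 1.18) the chances are 0.43 and 0.57, so the distortion is larger.

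**Main simulation.** 4,000 trials per scenario; four arms of 64; 15 mg set equal to placebo; 5 and 10 mg lower by 0.95; SD of change 1.3. Assumed, not in the documents: baseline normal(8.5, 0.9) truncated to 7–11%; Week 40 slope on baseline 0.4; eight post-baseline visits; AR(1) correlation 0.8 between adjacent visits; 30% SGLT-2i use; placebo Week 40 means as shown. Unstructured MMRM, then the stated logistic model. Type I error is 15 mg against placebo at nominal 5%; bias is in the 10 mg minus placebo difference, in percentage points. Rescue-driven missingness removes data after Week 24 for everyone with HbA1c ≥8.5% then and, in the words of Protocol 8.3.4.2 criterion (c), "inadequate response to the existing regimen defined as improvement in HbA1c over the last 3 months" below 0.3%; this is capped at 25% per arm and topped up with random dropout.

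Cut-off <7.0%, 25% missing, conditional prediction:

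| Placebo mean | 7.0 | 7.45 | 8.0 | 8.5 |
|---|---|---|---|---|
| Type I %, full data | 4.9 | 5.1 | 5.0 | 3.8 |
| Type I %, random dropout | 13.6 | 11.1 | 6.1 | 3.2 |
| Type I %, late dropout | 9.2 | 8.2 | 6.3 | not run |
| Type I %, rescue-driven | 10.2 | 7.0 | 4.3 | 3.4 |
| Bias, random dropout | +3.4 | +6.1 | +3.2 | −1.0 |
| Bias, late dropout | +2.1 | +3.1 | +2.1 | not run |
| Bias, rescue-driven | +3.5 | +4.1 | −0.1 | −1.6 |

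Other cut-offs, random dropout, same four means:

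- ≤6.5%: type I 11.1 / 6.8 / 3.4 / 0.4% (full data 5.0 / 4.2 / 3.8 / 1.1%); bias +6.2 / +3.7 / −1.0 / −2.3.
- <5.7%: no inflation; bias +0.5 / −2.0 / −1.9 / −1.3.

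Sensitivity, <7.0%:

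- 10% random missing at 7.0 / 7.45 / 8.0: type I 7.9 / 6.9 / 5.2%; bias +1.3 / +2.5 / +1.3.
- 10% rescue-driven at 7.45: type I 4.3%, bias +0.8.
- Correlation 0.9, 25% random, 7.45: type I 7.6%, bias +3.1.
- Marginal prediction, 25% random, all four means: type I 23.2 / 13.7 / 4.1 / 2.4%; bias +5.0 / +12.3 / +4.7 / −3.7.

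**Agreement across separate simulations.** A second simulation (5,000 null trials, six visits, correlation 0.85 per 8 weeks, 25% missing completely at random, conditional) gave type I of 10.8 / 9.8 / 8.0 / 6.4% at means 7.0 / 7.3 / 7.6 / 8.0. With placebo 7.5 and dose 6.55, a true difference of 30.0 points at <7.0% became 34.5, and 17.4 points at <5.7% became 16.1. A third (700 trials, 25% random, conditional) gave 15.4 / 10.7 / 5.1% at 7.0 / 7.45 / 8.0, with bias +3.9 / +6.4 / +2.9; at correlation 0.9 the 10.7% fell to 6.4%.

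**Family-wise error.** Case: 15 mg inert, 10 and 5 mg effective, weight gates assumed passed, 25% missing, means 7.0 / 7.45 / 8.0 / 8.5. Random 8.5 / 6.9 / 4.3 / 3.1%; late 6.2 / 5.5 / 4.5% (8.5 not run); rescue-driven 6.8 / 4.3 / 3.5 / 3.1%; full data 4.0 / 3.8 / 3.8 / 2.9%. At 10% random: 5.7 / 4.9 / 4.5% for the first three. The Monte Carlo SE at 5.5% is √(0.055 × 0.945 / 4000) = 0.36 points, so the late-dropout 5.5% is not distinguishable from 5%.

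**The case against.** The strongest reply is that the largest figures come from the least favourable setting. The 25% is a ceiling and includes rescue, and Protocol 8.3.4.2 does not allow rescue to be considered until about Week 16 and ties it to high glucose. Outcome-independent dropout spread over all visits is therefore a pessimistic pattern. Correlation, baseline distribution and placebo mean are all assumed. This stands: it limits the size, but not the mechanism, which appears in three separately built simulations.

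A reader might infer that the nominal level fails whenever the placebo mean is within half a point of any cut-off. The runs do not support that: 10% rescue-driven missingness at 7.45 showed no inflation, and <5.7% showed none in any scenario. A reader might also infer that the rule always favours tirzepatide. It does not; the bias turns negative when both arms lie well to one side of the cut-off.

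Nor is trial-wide error control broken. A false responder claim requires one high dose to be inert while the other and 5 mg succeed on HbA1c and weight. Even then the excess over 5% is confined to placebo means close to 7.0, or 7.45 under random dropout at 25%.

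Finally, a reader might conclude that the confirmatory test is unidentified. The SAP never states which analysis feeds Section 2.1. However, the longitudinal model is brought in as an addition, and Protocol 9.3.4 names the plain logistic model, so the ordinary reading is clear. The missing statement is secondary.

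**Conclusion.** The concern holds in limited form. The single-prediction rule understates the standard error and biases the responder difference. With 25% missing at random, adjacent-visit correlation 0.8 and conditional prediction, per-test type I error for <7.0% is about 11 to 15% within about 0.5 points of the cut-off and about 5 to 6% at 1 point. The difference is shifted by about +3 to +6 points at placebo means 7.0 to 8.0, and slightly downward further away. Lower missingness, higher correlation and rescue-driven missingness all reduce this, in one run to nothing; marginal prediction makes it worse near the cut-off. Family-wise error is affected only marginally and in a narrow case. The primary endpoint and the continuous key secondaries do not use the rule. Confidence in the mechanism is high; confidence in the size is moderate, because the placebo mean, correlation and dropout pattern are assumptions. The point is worth fixing mainly because gating does not protect the reported responder differences.

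**What to change.** In SAP 4.4.1.4, for the efficacy estimand, replace the single predicted value with multiple imputation of continuous Week 40 HbA1c under missing at random, consistent with the 4.3.2 MMRM: parameter and residual draws, conditional on earlier visits. Dichotomise each completed data set, fit the stated logistic model and combine by Rubin's rules. State that this analysis supplies the Section 2.1 p-value and that the longitudinal logistic model is supportive. Make the matching change in 4.4.2.2, imputing the weight-loss endpoints from the body-weight MMRM of 4.4.1.2.

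Cost: SAP wording and new code, since SAP Appendix 1 contains only missing-not-at-random programs. Protocol 9.3.4 sets no efficacy-estimand missing-data rule for these endpoints.

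In the main simulation, multiple imputation brought the difference to within 0.4 points of full data wherever it was run (25% random at all four means; 25% rescue-driven at 7.45 and 8.0; 10% random at 7.45; not late dropout). The tests become conservative: type I for <7.0% under 25% random was 3.4 / 3.3 / 2.2 / 1.0%.

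Power of 10 mg at 0.05 for <7.0%, ≤6.5%, <5.7%:

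- Random 25%, placebo mean 7.45: 88, 86, 67% with multiple imputation; 97, 95, 71% with the single value; 94, 92, 79% with full data. For the first two cut-offs, part of the loss is power beyond what complete data would give.
- Rescue-driven 25%, mean 8.0: 88, 82, 36% with multiple imputation against 90, 78, 28%, so power is not always lost.

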4.1. General Considerations

Statistical analysis of this study will be the responsibility of Eli Lilly and Company (Lilly) or its designee. The statistical analyses will be performed using SAS® (Version 9.4 or higher) and R® (Version 4.3.2 or higher).

Any change to the data analysis methods described in the protocol will require an amendment ONLY if it changes a principal feature of the protocol. Any other change to the data analysis methods described in the protocol, and the justification for making the change, will be described in the statistical analysis plan or clinical study report. Some analyses and summaries described in this analysis plan may not be conducted if not warranted by data (for example, few events to justify conducting an analysis). Listings of events will be provided in such situations. The primary analysis will be performed at database release after Last Participant Last Visit (LPLV). Additional analyses of the data may be conducted as deemed appropriate without further changes made to the protocol or SAP, even after the primary or final database locks.

Additionally, to avoid potential selection biases, unless stated otherwise, statistical summaries and analyses will be conducted based on randomized maintenance dose regardless of the actual treatment received by the patient.

Unless specified otherwise, the last measurement during Visit 1 to Visit 3 (including unscheduled visits) collected prior to or on the first dose day will serve as baseline.

- For lab and ECG, baseline needs to be prior to or within one hour after the first dose time.
- For patient-reported outcomes, data collected at Visit 3, regardless of the timing relative to first dose, will serve as baseline.

All tests of treatment effects will be conducted at a 2-sided alpha level of 0.05, unless otherwise stated, and all confidence intervals will be given at a 2-sided [95%] level. To avoid potential selection biases, unless stated otherwise, in statistical summaries and analyses, all data will be analyzed by randomized treatment assignment.

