There will be 2 estimands of interest in evaluating the primary and secondary efficacy objectives. The first estimand, the “efficacy” estimand, represents efficacy prior to discontinuation of study drug without the confounding effects of rescue therapy for severe persistent hyperglycemia. Analyses relative to the “efficacy” estimand will be conducted using the efficacy analysis set (EAS). The second estimand, the “treatment-regimen” estimand, represents the efficacy irrespective of adherence to investigational product or introduction of rescue therapy for severe persistent hyperglycemia. Analyses relative to the “treatment-regimen” estimand will be conducted using the full analysis set (FAS).

Safety will be assessed using Safety Analysis Set. Selected safety analyses may be conducted after excluding data on rescue therapy or data after starting another antihyperglycemic medication.

A listing of patients randomized but not included in efficacy analyses (not treated or discontinued treatment due to inadvertent enrollment) will be provided.

End of study participation for a patient will be the earliest of date of death, date of withdrawal from further participation in the study, or date of safety follow up visit (Visit 801). For patients considered to be lost to follow-up, end of study participation will be the date of lost to follow-up reported by the investigator. Patient data included in the database after the last date of study participation (date of death, date of early discontinuation or date of safety follow-up) will be excluded from statistical analysis. Listings of such data may be provided.

Summary statistics for continuous measures may include sample size, mean, standard deviation, median, minimum, and maximum.

The Kaplan-Meier method may be used for estimation of cumulative event-free survival rates over time, and Cox proportional hazards regression analysis will be used to compare hazard rates among treatments.

Summary statistics for categorical measures, including categorized continuous measures, will include sample size, frequency, and percentages. Fisher's exact test will be used to examine the treatment difference in categorical outcomes. Logistic regression may be used to examine the treatment difference in binary efficacy outcomes. The negative binomial regression model will be used for the treatment comparison of discrete count measures if deemed appropriate.

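### The confirmatory HbA1c <5.7% tests use ordinary logistic regression with no named test and no zero-responder rule; with no placebo responders a converged Wald test cannot reject

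*SAP*

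**What the plan says.** SAP 2.1, step 4, puts the <5.7% hypotheses H15,6, H10,6 and (as listed in that step) H5,6 at the end of a sequence in which hypotheses "will be evaluated hierarchically each at two-sided 0.05 significance level conditioned on the successfully achieving the preceding objective"; step 4b uses 0.025 instead.

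SAP 4.4.1.4 gives the analysis. Under both estimands the week-40 value is completed, dichotomised and modelled: "After dichotomizing, the data is analyzed using a logistic regression model which include treatment, SGLT-2i use (Yes or No) as fixed effects", with baseline HbA1c as covariate. For the treatment-regimen estimand, "Statistical inference over multiple imputations will be guided by Rubin (1987"). An additional longitudinal logistic model is planned for the efficacy estimand, and the section's only sparse-data provision belongs to it: "In case the longitudinal logistic model does not converge due to small number of events, logistic regression will be utilized". Protocol 9.3.4 names the same logistic regression and adds nothing on the test.

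Three general clauses in SAP 4.1 come near the question. The first concerns Fisher's method, whose "exact test will be used to examine the treatment difference in categorical outcomes". The second is only permissive: "Logistic regression may be used to examine the treatment difference in binary efficacy outcomes". The third lets analyses lapse; they "may not be conducted if not warranted by data (for example, few events to justify conducting an analysis").

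**The concern.** Few participants on placebo may reach HbA1c below 5.7%. Entry requires at least 7.0% at screening (Protocol 5.1), so a responder must fall by more than 1.3 points from the lowest eligible value. Placebo participants do titrate glargine, so the rate is unknown, but an empty placebo cell among 64 is a realistic outcome.

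In that case the maximum-likelihood log odds ratio does not exist (separation). The few-events sentence does not help, because it applies to a different model and falls back on the same regression. The general clauses do not settle the matter either: the Fisher clause is generic, while 4.4.1.4 specifically prescribes logistic regression, and the clause on dropping analyses does not say what then happens to the hierarchy.

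At stake are the <5.7% claims. A large, real difference could go unclaimed because placebo had no responders, or the test might be chosen after the counts were seen.

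**Working it through.** **1. The plan's own figure.** SAP 5 assumes a difference of 0.95, SD 1.3, two-sided alpha 0.025 and up to 25% rescue or discontinuation. A two-sample t-test with 48 per arm has 90.2% power; 48/0.75 = 64; 4 × 64 = 256. This reproduces. There is no corresponding figure for the <5.7% endpoint.

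**2. Chance of an empty placebo cell.** (1 − p)^64 for assumed p = 1, 2, 3, 5% gives 53, 27, 14, 4%.

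**3. What the Wald test does.** Unadjusted, with a placebo and b treated responders, SE² = 1/a + 1/(64−a) + 1/b + 1/(64−b). At a = 0 the estimate and SE are both infinite. One four-arm fit with the SAP terms and 0, 6, 8, 10 responders (placebo, 5, 10, 15 mg) gives for 15 mg:

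| Iteration | Estimate | SE | Wald p |
|---|---|---|---|
| 3 | 2.47 | 1.08 | 0.023 |
| 5 | 4.49 | 2.80 | 0.11 |
| 8 | 7.49 | 12.43 | 0.55 |
| 15 | 14.49 | 411.59 | 0.97 |
| 25 | 24.49 | 61,084 | 0.9997 |

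Each later iteration adds about 1 to the estimate and multiplies the SE by about 1.65, so z tends to 0. On the same data ordinary likelihood ratio (LR) gives p = 0.00015, Firth penalised LR 0.0006 and Fisher 0.0013. In 2,607 simulated trials with no placebo responders (tolerance 1e-8, at most 25 iterations) the Wald test never rejected.

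**4. Power, efficacy estimand.** All 65 × 65 outcomes were enumerated with 64 per arm, unadjusted, at two-sided 0.05, counting Wald with an empty cell as non-significant. Against 0/64 Firth penalised LR rejects from 5 treated responders, so the zero-cell part of the gap is (1 − p0)^64 × P(B ≥ 5), where B is the treated count.

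| Placebo vs tirzepatide | Wald % | Firth LR % | Gap | Zero cell | Rest |
|---|---|---|---|---|---|
| 1 vs 15% | 33.7 | 88.5 | 54.8 | 51.1 | 3.7 |
| 2 vs 15% | 46.4 | 78.0 | 31.6 | 26.7 | 4.9 |
| 3 vs 15% | 47.9 | 66.9 | 19.0 | 13.8 | 5.2 |
| 5 vs 15% | 37.9 | 45.9 | 8.0 | 3.6 | 4.4 |
| 2 vs 25% | 71.2 | 99.0 | 27.8 | 27.4 | 0.4 |

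The last column is the effect of using LR rather than Wald at small non-zero counts: against 1/64, Wald needs 8 treated responders and Firth LR 7.

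**5. Type I error at 0.05, equal rates.** Ordinary LR: 2.8, 7.6, 9.3, 7.9% at 1, 2, 3, 5%. Firth penalised LR: at most 2.9%.

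**6. Treatment-regimen estimand.** Rubin's total variance is W + (1 + 1/m)B, where W is the mean within-imputation variance, B the between-imputation variance and m the number of imputations. One separated data set fitted to 25 iterations, as in step 3, contributes 61,084²/m to W. That is an SE of about 13,660 at m = 20 and still about 1,930 at m = 1,000, so no practical m rescues the test.

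Simulation used 20 imputations and assumed 25% discontinuation, 60% of those retrieved, and half the effect kept afterwards. At placebo 2%, 30–33% of trials had at least one separated imputation. Over all rates studied, pooled maximum likelihood was significant in 0 of 4,390 such trials, at 8 or 25 iterations. Power, pooled maximum likelihood versus pooled Firth: 2 vs 15%, 37.5 vs 55%; 2 vs 25%, 63 vs 94.5%. These figures cover only the 87–90% of trials that used retrieved-dropout imputation.

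**The case against.** The strongest defence is that the consequence is narrow. These tests come last, so nothing higher in the sequence is lost. The only route back is step 5 ("recycle 100% of the unused alpha back to #1 or #2 above"), which matters only if a step 1 or 2 objective had failed. All response rates are assumed, and at a 5% placebo rate little is lost. This stands.

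Several stronger readings are tempting and do not hold:

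- *The software's iteration limit decides the claim.* The p-value does move with the stopping rule, but in step 3 it is below 0.05 only at iterations 2 to 4. At ordinary settings the decision is a stable non-rejection. Early stopping changed the pooled decision only in a constructed case: 16/64 treated, placebo 1/64 in every imputation but one and 0/64 in that one, fits stopped at 8 iterations. Pooled p was 0.30, 0.069, 0.030 and 0.007 with 20, 100, 200 and 1,000 imputations.
- *The whole power gap comes from the zero cell.* At 5 vs 15% more than half of it is test choice.
- *Ordinary LR always rejects too often.* At a 1% common rate it is conservative.
- *The treatment-regimen figures are general.* SAP 5 gives 25% as an upper limit. At 10% discontinuation, 64 × 0.10 × 0.60 = 3.8 retrieved dropouts per arm, so the rule in SAP 4.3.4 for four or fewer would usually switch to placebo-based imputation, for which no results are reported here.

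Firth regression is also partly a preference. Any prespecified statistic with a zero-responder rule that also covers imputed data sets would close the gap.

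**Conclusion.** The point holds as a loss of power in the last confirmatory tests. SAP 4.4.1.4 leaves the test statistic open for the efficacy estimand, implies a Wald test for the treatment-regimen estimand, and has no rule for an empty placebo arm under either. If the test is Wald, H15,6, H10,6 and H5,6 as listed in step 4 cannot be rejected under the efficacy estimand when placebo has no responders, and will generally fail under the treatment-regimen estimand once any imputed data set has none.

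The zero-cell cost is at most the chance of 0/64: about 51 points at 1 vs 15%, 27 at 2 vs 15% or 2 vs 25%, 14 at 3 vs 15%, and 4 at 5 vs 15%. These figures rest on assumed rates, 64 per arm, complete data and no covariates. A reader might infer a risk of false positive claims; nothing here supports that for the Wald test at ordinary convergence. The sponsor should settle this before unblinding; it does not threaten the primary result.

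**What to change.** In SAP 4.4.1.4, for the <5.7% endpoint, prespecify before unblinding Firth penalised logistic regression with the same terms, used whatever the counts turn out to be.

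- Efficacy estimand: penalised likelihood-ratio p-value and profile interval.
- Treatment-regimen estimand: Firth estimate and SE from each imputed data set, pooled by Rubin's rules, with the number of imputations stated (the code in SAP 7.1 leaves it as a macro variable).

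The cost is SAP wording. There are two downsides: the odds ratio is slightly shrunken, and the pooled Firth test is a Wald test that is conservative at low treated counts. Against 0/64 (unadjusted, complete data) Firth-Wald needs 8 treated responders at 0.05 and 11 at 0.025; Fisher needs 6 and 7, and Firth penalised LR 5 and 5. Fisher drops the covariates and supplies no estimate and SE to pool. Ordinary LR would avoid separation in the efficacy analysis, but exceeds 5% at the 2, 3 and 5% common rates shown above.
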